12.0 Statistical Plan

12.1 Sample Size Determination

Primary and secondary outcomes will be analyzed at the conclusion of the trial.

A table of sample sizes for time from randomization to first successful extubation/liberation is shown below. These calculations incorporate death by treating death as censoring. The current hazard rate for death is used in this calculation. The final column is obtained by dividing the "Total N" column by 0.95 to account for the 5% dropout. Assuming this increase is sufficient to observe the required number of events in the presence of the drop-out, it should be a reasonable target.

All calculations are using 80% power and 2-sided Type I error of 5%. Exponential survival is assumed for the purposes of hazard calculations. The expected median time to extubation in PAV is determined from the PSV value by converting to the hazard scale, multiplying by the hazard ratio and converting back to time.

Median Time (PSV)	Median Time (PAV)	Difference	Hazard Ratio	Required Events	Total N	Total N (5% lost)
7.40	6.17	1.23	1.20	944	1095	1153
7.40	5.92	1.48	1.25	630	729	768
7.40	5.69	1.71	1.30	456	526	554
7.50	6.25	1.25	1.20	944	1097	1155
7.50	6.00	1.50	1.25	630	731	770
7.50	5.77	1.73	1.30	456	527	555
7.55	6.29	1.26	1.20	944	1098	1156
7.55	6.04	1.51	1.25	630	731	770

7.55	5.81	1.74	1.30	456	528	556
7.60	6.33	1.27	1.20	944	1099	1157
7.60	6.08	1.52	1.25	630	732	771
7.60	5.85	1.75	1.30	456	528	556
7.70	6.42	1.28	1.20	944	1101	1159
7.70	6.16	1.54	1.25	630	733	772
7.70	5.92	1.78	1.30	456	529	557

As planned a priori, we used aggregate, blinded data from the first 120 patients to re-estimate our sample size. Using a time to event analysis, median time to successful liberation in the entire cohort was 6.8 days. The minimum clinically important difference in time to successful liberation is deemed to be 1.0 day. Using a hazard ratio of 1.30, to demonstrate a reduction in the median duration of ventilation by 1.78 days (assuming 7.70 days versus 5.92), alpha of 0.05 (two-sided) and a power of 80%, requires 529 patients. Anticipating a maximum loss to follow-up (e.g. consent withdrawn) rate of 5%, 558 patients (279 per group) should be randomized in the study. Using a hazard ratio of 1.25, to demonstrate a reduction in the median duration of ventilation by 1.51 days would require 770 patients (385 per group) to be randomized in the study.

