For days requiring A/C, patients not receiving A/C will be assigned a value of zero. Although a t-test is the appropriate parametric approach, the non-parametric Wilcoxon rank-sum will be favoured if there are many 'null' (zeros) entries. Total medication dose, pain, agitation, and delirium scores will be compared by a t-test between study arms. Ordinal regression analyses will be used to assess factors associated with weaning group classification (short/difficult/prolonged weaning groups). Exploratory analyses using multiple regressions will be used to identify factors associated with duration of MV.

The secondary outcome of Ventilator-Free Days (VFD) has a number of difficulties, one of which is that death is indistinguishable from someone alive at day 21 but still ventilated. Analysis of survivors only results in an improper sub-group and potentially loses the benefits of balanced confounders due to randomization. Therefore a number of secondary and supplemental analyses are planned to fully understand any observed treatment effect. One analysis will assign -1 to deaths (instead of zero) to make that distinction. We will also examine time on ventilator in a number of ways (some of which subsume secondary outcomes). A Poisson regression model can be used which considers number of days on ventilator as the outcome and uses the logarithm of the number of days observed (up to 21) as an offset. Another analysis will consider time to extubation as the outcome with death treated as a competing risk. Cumulative incidence curves will be produced and suitable competing risks survival model will be used to estimate a treatment effect. Finally, a marginal structural model will be employed where first the probability of surviving will be modeled and then the weighted analysis of the survivors will be carried out using the inverse of the survival probability as the weight.

There are 4 planned subgroup analyses based on: (a) duration of MV prior to randomization greater than 5 days, which is associated with prolonged weaning; (b) failed SBT prior to randomization, depicting a subgroup classified as difficult weaning vs. failed CPAP 0 trial vs. failed weaning criteria prior to randomization; (c) failed extubation prior to randomization, depicting a subgroup classified as difficult weaning; and (d) mild vs. moderate vs. severe frailty.

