2.3 Sample Size

Sample size was calculated based on the primary outcome of time to first successful liberation from mechanical ventilation. The calculation treated death as a censoring event. Sample sizes assuming a hazard ratio ranging between 1.2 to 1.3 were calculated. We used 80% power and a 2-sided type I error of 5%. We also assumed a 5% rate of dropout.

As planned a priori, aggregate blinded data from the first 120 patients was used to re-estimate the sample size. Median time to successful liberation in the entire cohort was 6.8 days. The minimal clinically important difference was deemed to be 1 day. Assuming a hazard ratio of 1.3, to demonstrate a reduction in the median

duration of ventilation by 1.78 days, we will require 529 patients or 558 patients if we assume a loss to followup of 5%. Assuming a hazard ratio of 1.25 will require 770 patients to demonstrate a difference of 1.5 days (Table xx). We expect to enroll a minimum of 558 patients within the planned 5 year of enrollment.

Median Time (PSV)	Median Time (PAV)	Difference	Hazard Ratio	Required Events	Total N	Total N(5% lost)
7.40	6.17	1.23	1.20	944	1095	1153
7.40	5.92	1.48	1.25	630	729	768
7.40	5.69	1.71	1.30	456	526	554
7.50	6.25	1.25	1.20	944	1097	1155
7.50	6.00	1.50	1.25	630	731	770
7.50	5.77	1.73	1.30	456	527	555
7.55	6.29	1.26	1.20	944	1098	1156
7.55	6.04	1.51	1.25	630	731	770
7.55	5.81	1.74	1.30	456	528	556
7.60	6.33	1.27	1.20	944	1098	1157
7.60	6.08	1.52	1.25	630	731	771
7.60	5.85	1.75	1.30	456	528	556
7.70	6.42	1.28	1.20	944	1101	1159
7.70	6.76	1.54	1.25	630	733	772
7.70	5.92	1.78	1.30	456	529	557

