3.1 Regarding P-Values and Statistical Significance

Controversy continues to exist around the use of p-values and significance testing. The problems are not so much the fault of p-values themselves but arise in the mechanical comparison to an arbitrary threshold of say 0.05 which categorizes results into, "statistically significant" or "not statistically significant." It is in this binary decision that the Type 1 error arises and the risk of making any Type 1 error among all tests increases with the number of tests. It is this problem that leads many to adjust p-values (or equivalently the threshold per test) in analysis.

However, the p-value as it stands simply represents a continuous measurement of the strength of the statistical evidence one has against some hypothesis (no difference between groups in this instance). It is thus best

statistical practice to report for all outcomes analyzed, the estimated treatment effect, the 95% (or some other suitable level) confidence interval (CI) and the p-value. This is the practice that will be adopted in the analysis. This gives a reader all of the necessary information to put the results into proper context. Note that the policy of some journals to request only the CI does not solve the problem it is intended to solve. Specifically, a reader will still mentally make the "significance conclusion" entirely through the CI.

Finally, the ASA statement on p-values [24] recommends all computed p-values be reported to provide sufficient context to evaluate the evidence in totality.

Treatment effect estimates will be reported with their 95% confidence intervals.

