6.2 Secondary Outcomes

The outcomes related to weaning progress and difficulties (listed below) also suffer from the competing risk of death and other improper subgroup issues. and will be looked at primarily descriptively.

- Time to death: will be analyzed using standard methods for survival data namely Kaplan-Meier curves and log-rank test. Treatment effects will be reported as hazard-ratios with 95% confidence intervals.
- Time from randomization to live ICU discharge (up to day 90) and time from randomization to live hospital discharge (up to day 90): Those two outcomes both have death as a competing risk. Cumulative incidence curves will be constructed to provide estimates of live ICU discharge and live hospital discharge that account for death. Cause-specific treatment effects on live ICU discharge and live hospital discharge will be reported as hazard ratios with 95% confidence intervals from Cox proportional hazard models.
- Time from randomization to first SBT, first successful SBT, and first extubation: These will be looked at primarily descriptively using cumulative incidence curves with death as a competing risk and compared across groups using the Gray's test.

• Ventilator-free days:

Ventilator-free days will be compared across groups using a Wilcoxon test. The treatment effect will be expressed as the difference in median ventilator-free days and its 95% confidence interval will be estimated using bootstrap methods. As per the calculation above, subjects might have 0 ventilator-free days because either they died before being liberated or they survived but remained ventilated. We

will model this using a number of approaches. For the primary analysis, we will assign the value -1 ventilator free days to subjects who died prior to liberation.

The following secondary analyses are also planned to help understand any observed treatment effect.

- Assigning the value of zero ventilator-free days to patients who died prior to being liberated from ventilation and performing a Wilcoxon test
- Poisson regression of the number of days on ventilator with the logarithm of the number of days observed as an offset
- Marginal structural model where first the probability of surviving will be modeled and then the
 weighted analysis of the survivors will be carried out using the inverse of the survival probability
 as the weight
- Invasively ventilated with tracheostomy and invasively ventilated with ETT

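### The Poisson regression of ventilator days has no provision for overdispersion; with default standard errors its CI would be under half its proper width at the protocol's 21-day cap

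*SAP*

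**What the plan says.** Under ventilator-free days, SAP 6.2 makes a Wilcoxon test the main comparison, scoring death before liberation as -1 and giving a bootstrap interval for the difference in medians. It then introduces supportive analyses: "The following secondary analyses are also planned to help understand any observed treatment effect". One of them is "Poisson regression of the number of days on ventilator with the logarithm of the number of days observed as an offset".

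Protocol 12.2 has the same model in looser terms: "A Poisson regression model can be used which considers number of days on ventilator as the outcome", and it "uses the logarithm of the number of days observed (up to 21) as an offset". The SAP does not carry over the 21-day limit.

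Neither document mentions overdispersion, a scale parameter, robust variance or a negative binomial alternative for this model. The bootstrap in SAP 6.2 belongs to the difference in medians. SAP 3.1 undertakes to report, for the outcomes analysed, "the estimated treatment effect, the 95% (or some other suitable level) confidence interval (CI) and the p-value".

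**The concern.** A Poisson model takes the variance of each patient's count to equal its mean. That suits independent events occurring at random. Ventilator days mostly come in runs: a patient ventilated today is very likely to be ventilated tomorrow. The spread between patients is therefore much wider than Poisson.

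The estimated rate ratio is still a sensible summary, namely ventilator days per day observed in one arm against the other. What fails is its precision. With default standard errors the interval is too short and the p-value too small. A tight rate ratio printed beside the Wilcoxon result could be taken as corroborating it, or as contradicting it, when it is neither.

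**Working it through.** **Inputs**
- Exponential durations: "Exponential survival is assumed for the purposes of hazard calculations" (Protocol 12.1).
- Pooled median: "Median time to successful liberation in the entire cohort was 6.8 days" (SAP 2.3). The design control median of 7.70 days was also tried.
- 279 patients per arm, hazard ratio 1.30, 456 events, N 529 (Protocol 12.1).
- Death hazard: not given, so back-solved below.
- Cap: 21 days (Protocol 12.2). As the SAP gives none, 14, 28 and 90 days were also tried.

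**The plan's own figure.** Schoenfeld events for hazard ratio 1.30: 4(1.960 + 0.842)² / (ln 1.30)² ≈ 456, as tabulated. 529/0.95 = 557, also as tabulated. These figures are not in dispute.

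**Death hazard.** With constant hazards the share liberated before death is λ/(λ + μ). Here λ = ln 2/6.8 = 0.1019 per day and the share is 456/529 = 0.862, so μ = 0.1019 × (529/456 − 1) = 0.0163 per day.

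**Mean and variance at 21 days.** Time on the ventilator ends at rate θ = 0.1019 + 0.0163 = 0.1182, so θc = 2.483 at c = 21.
- Mean = (1 − e^(−θc))/θ = (1 − 0.0835)/0.1182 = 7.75.
- Variance = (2/θ²)[1 − e^(−θc)(1 + θc)] − mean² ≈ 41.4.
- Rounding up to whole days gives mean 8.2 and variance 40. Poisson requires the two to be equal.

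**Standard error.** The default standard error of the log rate ratio is about √(2/(279 × 8.22)) = 0.030. Its true standard deviation in simulation is 0.064. The Pearson dispersion, which allows for the offset, is 4.25, and the standard error is too small by a factor of about 2.13. The interval is thus 1/2.13 = 47% of its proper width, and the implied two-sided error is 2Φ(−1.96/2.13) = 0.36.

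**Null simulation.** 4,000 trials per setting, no treatment effect, days observed counted to death or the cap. The error column gives the range over the runs made, which varied the median, the rounding of days and mortality after liberation.

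| Cap (days) | CI width, % of proper | Type I error, default SE |
|---|---|---|
| 14 | 61 | 23-30% |
| 21 | 47 | 35-39% |
| 28 | 41 | 41-47% |
| 90 | 31-32 | 50-56% |

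Sandwich standard errors gave about 5% at every cap. At 21 days quasi-Poisson gave about 6%, and negative binomial 3.5% (400 runs only).

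**Sensitivity at 21 days**
- Death hazard from 0 to 0.03 per day: 33-38%.
- No deaths after liberation: up to 40%.
- Weibull shape 0.7: 41-44%; shape 1.5: about 26%; shape 2: 15-17%; shape 3: about 5-6%.

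**Outside the model.** Protocol 4.4.1 reports pilot ICU stays of median 7.3 (IQR 5.2-11.4) and 12.4 (7.5-30.8) days. Poisson counts with those means would have IQRs of 5-9 and 10-15. ICU stay is only a related duration, but it too is wider than Poisson.

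**The case against.** Four stronger readings are tempting, and the documents do not support them.

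1. *The plan prescribes model-based standard errors.* It does not. It gives the outcome, the model family and the offset, and no variance estimator. The statistician may intend robust errors. The point is therefore conditional on the software default. It still stands, because nothing commits the analysis to anything else, and the choice should not be left until the data are seen.

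2. *SAP 3.1 demands a CI and p-value from every model.* Its undertaking is for outcomes, and the named test for this outcome is the Wilcoxon. SAP 3.1 also rejects mechanical comparison with 0.05, so a false declaration of significance is not how the plan intends to read results. However, it treats the p-value as a continuous measure of evidence and favours reporting all that are computed. A mis-scaled p-value or interval misleads on those terms too.

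3. *Ventilator days are one unbroken run, perfectly dependent.* Reintubated patients stay in the study (Protocol 8.3.5.2), and tracheostomy patients may have graded mask trials (Protocol 8.3.6). Days can be interrupted. Dependence is strong, not perfect.

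4. *The trial's conclusions are at risk.* The model is one of several supportive analyses of a secondary outcome, and the protocol says only that it can be used. Gray's test, the multistate Cox model, the sample size and the Wilcoxon analysis with its bootstrap interval do not rely on it.

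It is also fair to object that the exponential form was adopted only for the sample-size hazards, and that the size of the error moves with shape and cap. That is why ranges are given. The direction holds for every shape tried below about 3.

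**Conclusion.** The concern holds in conditional form. As written, the analysis makes no provision for overdispersion. If it is run with default Poisson standard errors, its interval and p-value will be materially wrong. At the protocol's 21-day cap the error rate is about 35-39% against a nominal 5%; over caps of 14 to 90 days it is about 23-56%.

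These sizes rest on exponential durations and on a back-solved death hazard that the documents do not state. They shrink if durations are more regular than exponential and largely disappear at Weibull shape about 3. The consequence is confined to this one supportive analysis. It should be corrected before analysis, but it does not bear on the primary result.

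**What to change.** In SAP 6.2, keep the rate-ratio model and the offset, and add that the CI and p-value will be based on robust (sandwich) standard errors. A quasi-Poisson or negative binomial model would also serve. State the observation window in the same line: either restore the protocol's 21 days or name another window and say why, since the window also defines the quantity estimated.

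The cost is one sentence in the SAP and one option in R. The interval becomes wider, by a factor of about 2.1 at 21 days, which is its proper width. Data collection, sample size and the primary analysis do not change.

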4.6.1 Intention To Treat Sample

All analyses will use the intention to treat sample. The intention to treat sample will be comprised of all randomized patients who started the study intervention, irrespective of compliance to their randomized group. Patients will contribute outcome data to the analysis based on the randomized group.

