5.2 Secondary Outcomes

The secondary outcomes are

- 1. Ventilator-free days at day 14, 21 and 28 post randomization
- 2. Time from randomization to live ICU discharge (up to day 90)
- 3. Time from randomization to live hospital discharge (up to day 90)
- 4. Mortality, measured as time to death, ICU mortality; hospital mortality; 21, 28, and 90 day mortality
- 5. Weaning Progress, measured as time from randomization to: first SBT; first successful SBT; first extubation or equivalent for tracheostomized patients.
- 6. Weaning Difficulties: Subjects will be classified in the 5 following groups according the WEAN Safe classification (calculated as time from first SBT/extubation):
 - (a) Successful liberation less than 24 hrs
 - (b) Successful liberation greater than 24 hrs but less than 7 days
 - (c) Successful liberation greater than 7 days
 - (d) Unsuccessful liberation alive but remain ventilator dependent at day 90
 - (e) Died prior to successful liberation
- 7. Weaning Complications, measured as the number of patients
 - used non-invasive ventilation post-extubation
 - ventilated more than 7 days post randomization
 - ventilated more than 21 days from time of randomization
 - ventilated more than 21 days from time of intubation (prolonged MV group)
 - receiving tracheostomy post-randomization
 - requiring re-intubation (up to 7d after planned extubation)
- 8. Safety and Tolerance of modes
 - Number of patients ever requiring A/C mode post randomization
 - Number of patient-days requiring A/C mode post randomization
 - Frequency and severity of reported serious adverse events across groups
- 9. Co-interventions are also monitored, including sedatives and anti-psychotic medications.

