- Number of patients successfully liberated in less than 24 hours since first SBT or first extubation attempt, number successfully liberated greater than 24 hours but less than 7 days, successfully liberated greater than 7 days, unsuccessful liberation (alive but remaining ventilator dependent at day 90), died prior to successful liberation. These outcomes will be compared across groups using the Chi-Square or Fisher's exact test.
- Delirium and sedation scores: Daily sedation scores will be analyzed as described in Section 5.5.2.
- Number of patients who received non-invasive ventilation post-extubation, ventilated more than 7 days post randomization, ventilated more than 21 days from time of intubation (prolonged MV group); receiving tracheostomy post-randomization, requiring re-intubation (up to 7d after planned extubation): These outcomes will be compared across groups using the Chi-Square or Fisher's exact test.
- Number of patients ever receiving A/C mode post randomization (Tolerance of modes): This outcome will be compared across treatment groups using Chi-Square or Fisher's Exact test and treatment differences will be reported as an odds ratio with 95% confidence interval. Patients not receiving A/C will be assigned a value of zero days. The non-parametric Wilcoxon rank-sum test will be favoured over the parametric t-test for this analysis if there are many zero days entries.

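### The SAP tests the counts ventilated more than 7 days and more than 21 days without a rule for deaths on the ventilator, so a mortality difference would bias both comparisons

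*SAP*

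**What the plan says.** SAP 5.2, item 7, introduces these outcomes as "Weaning Complications, measured as the number of patients" in each category. SAP 6.2 takes up two duration thresholds, "ventilated more than 7 days post randomization, ventilated more than 21 days from time of intubation (prolonged MV group"), and states: "These outcomes will be compared across groups using the Chi-Square or Fisher's exact test". The denominator is fixed by SAP 4.6.1: "All analyses will use the intention to treat sample". SAP 3.1 adds that an effect estimate, a confidence interval and a p-value are to be reported for every outcome analysed.

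Neither document gives a rule for a patient who dies while ventilated before day 7 or day 21. SAP 6.2 opens with a caveat about outcomes that "also suffer from the competing risk of death and other improper subgroup issues. and will be looked at primarily descriptively", but its sentence covers weaning progress and weaning difficulties and does not name weaning complications. Protocol 12.2 has a similar remark about four weaning-difficulty outcomes and names no test for the prolonged-ventilation counts, so the test comes from the SAP.

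SAP 5.2 also lists "ventilated more than 21 days from time of randomization", which has no entry in the SAP 6.2 analysis list.

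**The concern.** A patient who dies on the ventilator on day 3 was never ventilated for more than 7 days. In a two-cell table on the intention-to-treat denominator, that patient sits beside the patient extubated successfully on day 3. More deaths on the ventilator in one arm would therefore show as fewer prolonged-ventilation complications, and fewer deaths as more complications. The result can carry the wrong sign.

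The same SAP handles death explicitly in the neighbouring outcomes. Ventilator-free days give -1 to death before liberation. The weaning-difficulty classification has its own category for death. Discharge and first SBT or extubation are shown as cumulative incidence with death competing. The duration counts are the exception.

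**Working it through.** **Reproducing the plan's own figure.** The documents give no expected rate for either count, so the inputs come from the primary-outcome design row in Protocol 12.1 and SAP 2.3: hazard ratio 1.30, medians 7.70 and 5.92 days, exponential survival, 80% power, two-sided 5%.

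- Events: 4 × (1.960 + 0.842)² / (ln 1.30)² = 456, as stated.
- With 5% loss: 529 / 0.95 = 557, as in the table (the text says 558, or 279 per group).

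**Inputs for the illustration.**

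- PSV liberation hazard: λ = ln 2 / 7.70 = 0.0900 per day.
- Death hazard μ: Protocol 12.1 says one was used but does not print it. I solved for it so that the event fraction averaged over the two arms at 90 days equals 456/529 = 0.862. With PAV+ liberation at 1.30 × 0.0900 = 0.1170, μ = 0.0163 gives 0.847 (PSV) and 0.878 (PAV+), mean 0.862.
- Liberation is then set equal in both arms, so that any difference in the counts comes from death alone. The PAV+ death hazard is μ times an assumed ratio.

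**Formulas.**

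- Still ventilated at t: V(t) = exp(-(λ + μ)t).
- Died ventilated by t: D(t) = μ/(λ + μ) × (1 - V(t)).

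**Day 7.** In PSV, V = exp(-0.1063 × 7) = 47.5% and D = 0.1533 × 52.5% = 8.0%. The sum before rounding is 55.6%.

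| Assumed PAV+ death hazard ratio | Ventilated >7 days | Died ventilated | Dead or still ventilated |
|---|---|---|---|
| 1 (same as PSV) | 47.5% | 8.0% | 55.6% |
| 1.25 | 46.2% | 9.9% | 56.1% |
| 1.5 | 44.9% | 11.8% | 56.6% |
| 2 | 42.4% | 15.3% | 57.7% |

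The tested count falls down the table while the unfavourable total rises. With 279 per arm, the chance of a nominally significant result favouring PAV+ is about 9% at a ratio of 1.5 and 23% at 2.

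**Day 21 from intubation.** Assume 7 days of ventilation before randomization, so that the threshold falls at day 14 after it. In PSV 22.6% are still ventilated and 11.9% have died ventilated. At a death hazard ratio of 2 the count falls to 18.0%, while dead or still ventilated rises from 34.4% to 39.8%.

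**Sensitivity to the death hazard.** At a ratio of 2, moving the PSV death hazard from 0.008 to 0.025 per day changes the day-7 shift from -2.7 to -7.2 points.

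**The other direction.** SAP 7.3 assumes mortality of 23.1% on PSV and 18.9% on PAV+. Read as a hazard ratio, this is ln(1 - 0.189) / ln(1 - 0.231) = 0.80. Then V(7) on PAV+ = exp(-(0.0900 + 0.0130) × 7) = 48.6%, so PAV+ shows about 1 point more prolonged ventilation only because more patients survive.

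**The case against.** The strongest reply is that an excess of deaths could not stay hidden. The plan has Kaplan-Meier curves and a log-rank test for death, cumulative incidence of liberation with Gray's test, a multistate model with a dead state, ventilator-free days at -1 for death, a weaning classification with a category for death, and an ordinal 90-day status with death worst. SAP 3.1 also declines to read p-values against a threshold. This stands, and it limits the severity. It does not repair the two comparisons, which would still be reported with a test and could contradict the other analyses. The descriptive caveat helps only in part, because it does not name complications and a between-arm test is specified anyway.

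A reader might go further than the documents allow in three ways.

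- That the SAP counts early deaths as free of complication. It does not say so. That is the literal reading of a count with an intention-to-treat denominator and no rule for death.
- That more patients would score as not prolonged by dying than would have the complication. On the hazards above this is true at day 21 from randomization (10.7% still ventilated, 13.7% dead), but SAP 6.2 lists no test for that item. For 21 days from intubation the order reverses once prior ventilation exceeds about 2 days: the two are equal, at 13.3% each, on day 19 after randomization.
- That the plan foresees higher mortality on PAV+. Protocol 11.1 anticipates no added risk, and SAP 7.3 assumes lower mortality on PAV+. The ratio of 2 is only an illustration.

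It is also fair to say that a death-or-ventilated composite is a different outcome from the ventilation burden listed in Protocol 6.3. The fix does not require one.

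**Conclusion.** The point holds as a gap in the analysis of two secondary outcomes. No rule is stated for deaths before the threshold, and the literal count merges them with liberated patients, so a mortality difference in either direction biases the chi-square comparison. For death hazard ratios of 1.25 to 1.5 the shift at day 7 is about 1 to 3 points. At 2 it is about 5 points at day 7 and at day 14, with the sign opposite to that of dead or still ventilated. These sizes rest on constant hazards, a back-solved death hazard, equal liberation in both arms, assumed death hazard ratios and, for the 21-day item, 7 days of prior ventilation. The direction of the bias rests only on the literal count. The severity is modest: the change is worth making before analysis, and the primary conclusion does not depend on it.

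**What to change.** In SAP 6.2, for the two duration items, replace the two-cell test with one of the following:

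- a comparison by arm of three states at each threshold: liberated, still ventilated, died before liberation, using the SAP 5.1 definition of successful liberation; or
- the cumulative incidence of liberation at that time, with death as the competing event. The curves planned in SAP 6.1 run from randomization, so they give day 7 directly. For 21 days from intubation the threshold falls on a different day after randomization for each patient, so the three-state table is simpler.

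State that early deaths are not excluded, since exclusion would create the survivor-only subgroup that Protocol 12.2 warns against. The plain counts can stay as descriptive figures, so the outcomes listed in the protocol are kept. Also reconcile the item on 21 days from randomization: add it to SAP 6.2 on the same terms or remove it from SAP 5.2.

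The cost is one derived variable from data already collected, a few lines of SAP text and a slightly less simple summary.
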